5.5.1 Exposure-adjusted incidence rate and 100(1 - α)% confidence interval

Exposure-adjusted incidence rates is presented per 100 participant-years. Participant-years is calculated as a sum of individual participant durations in days divided by 365.25.

It will be assumed that for each of *n* participants in a clinical trial the time t_j , (j = 1, ..., n) to the first occurrence of a certain treatment emergent event is observed, or if the event was not experienced, the (censored) time to the end of the observation period or EOT, whichever occurs earlier. The sequence of first occurrences of an event will be modeled to follow approximately a Poisson process with constant intensity θ . The rate parameter θ will be estimated as $\lambda = D/T$, where $T = \sum_{j=1}^{n} t_j$ and D is the number of participants with at least one event. Conditionally on T, an exact $100(1 - \alpha)\%$ confidence interval for a Poisson variable with parameter θT and observed value D can be obtained based on (Garwood, 1936), from which an exact $100(1 - \alpha)\%$ confidence interval for $\lambda = D/T$ will be derived as follows (Sahai, 1993; Ulm, 1990):

Lower confidence limit
$$L = \frac{0.5\chi_{\frac{\alpha}{2},2D}}{T}$$
 for $D > 0$, and $= 0$ otherwise;

Upper confidence limit $U = \frac{0.5\chi_{1-\frac{\alpha}{2},2D+2}}{T}$.

where $\chi_{\alpha,k}$ is the α -th quantile of the Chi-square distribution with k degrees of freedom.

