Infections													A	As req	uired												
Hepatocellular carcinoma													A	As req	uired												
Malignancies													A	As req	uired												
Withdrawal of Informed Consent													A	∖s req	uired												
M12 Period completion ⁹													As re	equire	d												х

Page 77 of 136 Protocol No. CCFZ533A2202

Period														Treatr	nent							
Visit Name																						
Month		1 1.5 2 2.5 3 3.5 4 4.5 5 5.5 6 or FU 6.5 7 7.5 8 or FU 8.5 9 9 10 or FU 10.5 11 11.5 12 or FU																				
Day		1 1.5 2 2.5 3 3.5 4 4.5 5 5.5 FU 5.5 / 7.5 FU 5.5 9.5 OF 10.5 11 11.5 FU FU FU F															337					
Hour (h)	Pre	0	EOI +1h																			
Study completion ⁹													A	As req	uired							

@ = all assessment must be completed prior to the liver transplantation procedure.

S = Assessment to be recorded in source documentation, not in CRF.

X = Assessment to be performed/evaluated and recorded in CRF if applicable.

= to be performed once in a 48-hour period if Screening and Transplantation (Day 1) occur in close proximity.

EOI = End of infusion IV (administration), EOS = End of Study, EOT = End of Treatment

0 = Assessment can be done at home for Arm 1 participants and for Arm 2 and 3 participants receiving CFZ533 at home via a health care provider.

1. Graft vascular patency must be confirmed using appropriate imaging technology (e.g. Doppler ultrasound, angiography, angio MRI). Participants with any thrombosis or occlusion of hepatic artery, veins, portal vein or inferior vena cava or participants with no confirmatory imaging study cannot be randomized.

2. Assessment and specification refers to the physical examination. See Table 8-4 for detailed list of expected physical examinations.

3. Site must perform, at minimum, all assessments needed to evaluate participant's eligibility at screening and randomization.

4. Safety laboratory tests (central) from Baseline, Day 8±2 (Randomization), and at all visits indicated will include hematology, chemistry, coagulation and urinalysis as specified in Table 8-5. A-fetoprotein will be evaluated at Baseline, Day 8±2/Randomization (for HCC subjects, only) and as needed thereafter for recurrent and *de novo* cases. MMF trough levels will be collected at all visits indicated or unscheduled visit (dose change). At the time of biopsies, a chemistry central laboratory test should be performed and thereafter until the final outcome.

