2.1 Data analysis general information

Due to the early termination of the study, the analysis plan has been modified and may be different from the Protocol.

The primary analysis will be performed after all participants have completed the Month 12 visit, or prematurely discontinued study before Month 12. These analyses will be performed by a Contract Research Organization, ICON. Interim analyses, detailed in Section 2.13, will be performed also by ICON.

The following general data conventions will apply:

- Cut-off day is defined as the latest study day before or up to which data will be used in the • analysis. Note that safety data collected during the Safety Follow-up period after EOS is reported to Novartis/Safety and will be included in relevant analyses.
- Descriptive statistics will be calculated based on observed values. Missing values will be • presented separately for each parameter or category. Categorical data will be presented as frequencies and percentages. For continuous data, n (sample size), mean, standard deviation, median, 25th and 75th percentiles, minimum, and maximum will be presented.
- BPAR will be based on centrally blinded adjudicated data. All other efficacy • endpoints will also be based on central

lab data.

- AE, SAE, Infection, Serious Infection (including malignancies), CMV information, and • EBV information will be summarized based on all eligible collected events.
- All lab and vital sign tables will include data since baseline (liver Tx) but changes are calculated based on the day of randomization. All summaries are based on central lab data.

Novartis	
SAP	

- Efficacy and liver function analyses are based on all available data including those after study medication discontinuation or as a supportive analysis based only on on-treatment values. Participants are censored for the time-to-event analyses if they do not have an event. For on-treatment analysis, the censoring day is the date of discontinuation of study treatment (defined in Section 2.1.1); for the all-data analysis (regardless of on-treatment or off-treatment), the censoring day is the last contact day.
- Listings will only be provided for variables explicitly indicated in this SAP. Listings will include all available data.

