2.1.1 General definitions

For the purposes of statistical analysis, "study treatments" are and will be displayed in the outputs as CFZ533 300mg + MMF, CFZ533 600mg + MMF, and TAC + MMF. "Baseline" is defined as the last assessment, including unscheduled assessments, performed prior to liver Tx. All assessments obtained after liver Tx are considered as post-baseline unless otherwise specified. Only centrally adjudicated data will be used for efficacy analyses and laboratory (including vital signs).

In the event that a participant only takes one of the three treatments, the following definitions apply:

- Start of study treatment:
 - a. CFZ533 arms: day of the first loading dose of CFZ533 on Day 8±2 post-LTx.
 - b. Control arm: Day 8 post LTx.
- End of study treatment:
 - a. CFZ533 arms: day of the last dose of CFZ533 +14 days. If a participant in CFZ533 arms discontinues treatment before Day 8±2 (first dose of CFZ533), the rules of control arm apply.
 - b. Control arm: day of the last dose of TAC.

In calculating the duration of treatment, days of permitted interruption of study medication (CFZ, TAC, and MMF) for any reason will be included (see Section 6.5 in the Protocol for details on permitted dose interruption). The entire treatment period is divided into three parts: Treatment Period 1, 2, and 3 (see Section 1.1).

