2.7 Safety analyses

The SAF will be used for safety analyses unless otherwise specified. General safety summaries (tables, figures, etc.) will include only data from the on-treatment period with the exception of baseline data which will also be summarized where appropriate (e.g., change from baseline summaries), unless otherwise specified. For CFZ533 arms, the on-treatment period lasts from the date of first administration of study treatment to 14 days after the date of the last actual administration. For the Control arm, it lasts to the day of the last actual administration of TAC.

Adverse events (AEs) will be presented and summarized for all treatment-emergent events, with a start date after randomization and covering until 14 weeks after the last administration of CFZ533 for CFZ533 arms and 12 weeks after that of TAC for TAC arm. In addition, a separate summary for death will be provided. Malignancies are summarized under SAEs.

All information obtained on adverse events will be displayed by treatment group. The number and percentage of participants with treatment-emergent adverse events and serious adverse events (events started after the first dose of study medication or events present prior to start of treatment but increased in severity based on preferred term) will be summarized in the following ways:

- by treatment, primary system organ class and/or preferred term
- by treatment, primary system organ class, preferred term and/or maximum severity

Separate summaries will be provided for AEs leading to treatment discontinuation.

In addition, the proportion of participants with infections will be summarized as follows:

- Infections by type of infection (viral, fungal, bacterial, others) and severity.
- Serious infections by type of infection (viral, fungal, bacterial, others) and severity.

The incidence rate of infection by type (viral, bacterial, fungal, and others) will be tabulated for each treatment arm. The key safety parameter is serious infections. The number of serious infections will be used to evaluate the stopping rule as outlined in Section 9.1.5 in Protocol.

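### SAP 5.5.1 does not use one window for events and person-time: combined with the SAP 2.7 adverse-event window, exposure-adjusted rates are biased upward, more so where treatment is shorter

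*SAP*

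**What the plan says.** **The rate (SAP 5.5.1).** The estimate is D/T, where "D is the number of participants with at least one event". T sums, over participants, the time to the first treatment-emergent event. A participant without an event is censored at the "time to the end of the observation period or EOT, whichever occurs earlier". The section puts no upper limit on the date of a counted event.

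**The event window (SAP 2.7).** General safety summaries use on-treatment data unless otherwise specified. The next paragraph specifies otherwise for adverse events: they start after randomization, "covering until 14 weeks after the last administration of CFZ533 for CFZ533 arms and 12 weeks after that of TAC for TAC arm". The definition of treatment-emergent that follows has a start condition only: "events started after the first dose of study medication or events present prior to start of treatment but increased in severity".

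**End of treatment.** The SAP's abbreviation list does not include EOT. The legend to Protocol Table 8-1 gives "EOT = End of Treatment". SAP 2.1.1 fixes the day: "CFZ533 arms: day of the last dose of CFZ533 +14 days", and "Control arm: day of the last dose of TAC".

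**Data after treatment.** SAP 2.1 states: "Note that safety data collected during the Safety Follow-up period after EOS is reported to Novartis/Safety and will be included in relevant analyses".

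**Where the rates are scheduled (SAP 2.13).** The interim analysis presents adverse events, serious adverse events, infections, serious infections, deaths and safety topics for all participants as exposure-adjusted rates. The opening sentence of that section says that endpoints are analysed on on-treatment data, with listed exceptions.

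**The concern.** A person-time rate needs the same risk window above and below the line. Read with the treatment-emergent definition in SAP 2.7, a first event in the 12 weeks after end of treatment enters D. A participant who passes through those same 12 weeks without an event adds nothing to T. Time past end of treatment is therefore counted only for those who have an event.

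The resulting bias is upward, and it is larger when treatment is shorter because the missing 84 days are then a larger share of the total. Exposure adjustment is meant to remove the effect of unequal time on treatment, and here part of that effect would come back. The exact Poisson interval in 5.5.1 conditions on the same T and inherits the error.

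**Working it through.** The documents state no exposure-adjusted rate, so there is no figure to reproduce. The check is of the two windows and of what the mismatch does.

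**Length of the gap** (SAP 2.7 window minus SAP 2.1.1 end of treatment)

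- CFZ533 arms: 14 weeks − 2 weeks = 12 weeks
- TAC arm: 12 weeks − 0 weeks = 12 weeks

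So G = 84 days = 84/365.25 = 0.230 years in every arm.

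**Model.** Let h be a constant hazard per participant-year and τ the time on treatment in years. Everyone stops at τ, and events are fully captured to τ + G. Per participant:

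- P(event counted) = 1 − S, with S = exp(−h(τ + G))
- person-time on the matching window: A = (1 − S)/h
- person-time as 5.5.1 is written: W = A − G·S, because event-free participants (probability S) lose G
- inflation factor = A/W, which tends to 1 + G/τ for rare events

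The values of h and τ are assumptions; the documents give none.

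| h per PY | τ | 1 − S | A | W | A/W | rate as written |
|---|---|---|---|---|---|---|
| 0.2 | 3 months | 0.0915 | 0.4577 | 0.2487 | 1.84 | 0.37 |
| 0.2 | 12 months | 0.2181 | 1.0904 | 0.9105 | 1.20 | 0.24 |
| 0.6 | 6 months | 0.3547 | 0.5911 | 0.4427 | 1.34 | 0.80 |
| 0.6 | 12 months | 0.5219 | 0.8699 | 0.7599 | 1.14 | 0.69 |
| 1.2 | 3 months | 0.4378 | 0.3649 | 0.2356 | 1.55 | 1.86 |
| 1.2 | 12 months | 0.7714 | 0.6429 | 0.5903 | 1.09 | 1.31 |

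Inflation is thus 55% to 84% at 3 months and 9% to 20% at 12 months. With matched windows, (1 − S)/A returns h in every row.

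**Between arms.** Two arms with the same true rate of 0.6, one with 6 and one with 12 months on treatment, would show 0.80 and 0.69, a ratio of 1.17 where the truth is 1. With equal time on treatment and equal hazard, the factor is the same in both arms.

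**Simulation check.** At τ = 168 days and a true rate of 20 per 100 participant-years, simulation gives 29.03 and the formula 29.02.

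**Post-treatment hazard.** At τ = 84 days and an on-treatment rate of 20 per 100 participant-years:

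- halved after treatment: 29.3 as written against 15.1 matched
- unchanged: 38.3 against 20.0
- doubled: 55.0 against 29.7

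The direction is the same in all three.

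**Against a strictly on-treatment rate.** Each extra event after end of treatment adds at most 84 days to T. The extra events therefore come at no less than 365.25/84 = 4.35 per participant-year. The rate as written exceeds the on-treatment rate whenever the latter is below about 435 per 100 participant-years.

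**The case against.** The strongest reply is SAP 2.13. It is the only section that explicitly schedules exposure-adjusted rates, and it says on-treatment data. None of its listed exceptions extends safety events beyond end of treatment. On that reading D stops at end of treatment, T stops there too, and the interim rates are aligned. SAP 2.1.2 supports this with its on-treatment default for safety. The 14/12-week window in SAP 2.7 is attached to counts, percentages and proportions. Where 2.7 mentions incidence rates, it cites neither person-years nor 5.5.1.

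This stands as a possible reading, but the SAP does not settle it. The default in 2.1.2 yields where something else is specified, and 2.7 does so for adverse events. Section 5.5.1 uses the term that 2.7 defines and does not cap the event date.

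The second reply concerns size, and it also stands:

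- Under Protocol 10.1.1, non-serious events are collected only to the EOS visit. Under Protocol 3, control participants take their last TAC dose on the EOS day. For those treated to EOS there are no non-serious events after treatment to inflate D.
- Serious events are reported for the full 14 or 12 weeks (Protocol 10.1.3). For all events, substantial post-treatment capture needs a participant who stops drug and stays in follow-up, as Protocol 9.1.1 provides up to Month 24.
- A participant still on treatment at a data cut-off has no gap.

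Three stronger inferences are tempting, and the documents do not support them. First, that the interim rates, or the termination decision that followed the interim analysis, rested on inflated figures: 2.13 may well have limited events to on-treatment. Second, that 14 against 12 weeks favours one arm: the 14 days added to CFZ533 treatment make the gap 12 weeks everywhere. Third, that the final report contains affected rates: the SAP schedules no exposure-adjusted output for it.

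**Conclusion.** The formula is wrong as written when it is used with the SAP's own treatment-emergent window, and the SAP does not say whether it is to be used that way. If SAP 2.13 limits D to events by end of treatment, the interim rates are correct, and the problem is confined to any output that pairs 5.5.1 with the 2.7 window.

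Where the pairing applies, the bias is upward in every arm. It distorts the comparison between arms only if treatment duration differs. The percentages above show the upper end at each stated exposure. They rest on constant hazard, everyone stopping at that exposure, and full event capture for 84 days. The real effect is smaller for non-serious events in participants treated to EOS, and zero for anyone still on treatment at the cut-off. The matter concerns safety rates, not the primary endpoint.

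**What to change.** State in SAP 5.5.1 one window that governs both D and T. Either of these works:

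1. Count only first events on or before end of treatment, keep the present censoring, and label the result an on-treatment rate. This agrees with SAP 2.13.
2. Keep the 2.7 window for D, and censor event-free participants at the earliest of the end of that window, the last date on which that type of event was collected, and the data cut-off. The collection date matters because non-serious and serious events stop being collected at different times.

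SAP 2.13 should then name the option it uses, and EOT should be defined by reference to SAP 2.1.1. The cost is one or two sentences and a change to one derived censoring date or event flag. No new data are needed. If exposure-adjusted rates have already been produced, checking which event cut-off was programmed shows whether any need to be rerun.

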5.6 Rule of exclusion criteria of analysis sets

Table 5-9_displays the criteria for exclusions from analysis sets.

Table 5-9	Participant Classification		
Analysis Set	PD ID that cause participants to be excluded	Non-PD criteria that cause participants to be excluded	
SCR	INCL01	Not having informed consent;	
		Not having screening epoch disposition page	
FAS	INC03, OTH03, OTH10	Not randomized; Not transplanted;	
		Mis-randomized	
SAF	NA	No study drug taken	

Analysis Set	PD ID that cause participants to be excluded	Non-PD criteria that cause participants to be excluded
РК	NA	No study drug taken; PD with relevant impact on PK; no valid PK concentration measurement

6 Reference

Garwood, F (1936). Fiducial limits for the Poisson distribution. Biometrika, 46; 441–453.

Sahai H, Khurshid Anwer (1993). Confidence intervals for the mean of a poisson distribution: a review. Biom J, 35 (7); 857-867

Ulm K (1990). A simple method to calculate the confidence interval of a standard mortality ratio. American Journal of Epidemiology, 131(2); 373-375
